4.3. Medical History and Atopic Disease Medical History

Medical history will be coded to a Preferred Term (PT), high level term (HLT) and associated primary System Organ Class (SOC) according to the latest available version of MedDRA at the coding CRO.

The atopic disease (AD) medical history includes diagnosis of AD and AD treatment history, asthma, allergic conjunctivitis, allergic rhinitis, chronic rhinosinusitis, nasal polyps, eosinophilic esophagitis, food allergy hives and other allergies due to medications, animals, plants, mold, dust mites, etc. The AD medical history was collected through atopic / allergic disease history case report form (CRF) in the parent study and will be summarized in current study.

4.4. Pre-treatment / Concomitant Medications and Procedures

Medications/Procedures will be recorded from the day of informed consent until the EOS visit. Medications will be coded to the ATC level 2 (therapeutic main group) and ATC level 4 (chemical/therapeutic subgroup), according to the latest available version of WHO Drug Dictionary (WHODD) at the coding CRO. Patients will be counted once in all ATC categories linked to the medication.

Pre-treatment medications/procedures: medications taken or procedures performed prior to administration of the first study drug in current study.

Concomitant medications/procedures: medications taken or procedures performed following the first dose of study drug of current study through the EOS visit.

Treatment with the following concomitant medications is prohibited during the study:

- Treatment with nonsteroidal systemic immunosuppressive medications (including, but not limited to, cyclosporine, mycophenolate-mofetil, IFN- γ , azathioprine, methotrexate, or other immunomodulating biologics).
 - Systemic corticosteroids were removed as a prohibited medication as of Amendment 7.
- Treatment with an investigational drug (other than dupilumab)
- Live (attenuated) vaccines

FluMist Influenza	Rubella
Intranasal influenza	Smallpox (Vaccinia)
Measles (Rubeola)	Yellow fever
Measles-mumps-rubella (MMR) combination	Bacillus-Calmette–Guérin (BCG)
Measles-mumps-rubella-varicella (MMRV) combination	Rotavirus
Mumps	Varicella Zoster (shingles)
Oral polio (Sabin)	Chickenpox (Varicella)
Chickenpox (Varicella)	

If medically necessary, patients may receive prohibited medication(s) at the discretion of the investigator (e.g., as rescue treatment for intolerable AD symptoms or to manage serious intercurrent conditions). However, patients who receive prohibited medication(s) will be discontinued from study drug for the duration of treatment with these prohibited medications, plus 5 half-lives. These patients will be asked to continue with the assessments of the early termination and end of study visits.

4.5. Efficacy Variables

Analysis of efficacy variables will be performed in the overall SAF population, as described in Section 3.1.

Starting from protocol amendment 6, the following assessments were removed from the schedule of events. All available data collected prior to implementation of protocol amendment 6 will still be summarized.

- POEM
- Dermatology Life Quality Index (DLQI)
- EQ-5D
- Patient Global Assessment of Disease Status
- Patient Global Assessment of Treatment Effect

All efficacy related endpoints for this study are secondary endpoints. Secondary endpoints include:

- Key secondary endpoints
 - Proportion of patients with IGA score of either 0 or 1 at each visit
 - Proportion of patients with EASI-75 relative to baseline of parent study ($\geq 75\%$ reduction in EASI scores from baseline of parent study) at each visit
- Other secondary endpoints
 - Proportion of patients with low disease activity state (ie., IGA ≤ 2) at each visit
 - Proportion of patients achieving an IGA reduction of ≥ 2 from Day 1 of current study at each visit for patients with Day 1 IGA score of current study ≥ 2
 - Percentage change from Day 1 of current study in EASI score at each visit
 - Percentage change from baseline of parent study in EASI score at each visit
 - Change from Day 1 of current study in EASI score at each visit
 - Change from baseline of parent study in EASI score at each visit
 - Proportion of patients with EASI-50 relative to baseline of parent study ($\geq 50\%$ reduction in EASI scores from baseline of parent study) at each visit
 - Proportion of patients with EASI-90 relative to baseline of parent study ($\geq 90\%$ reduction in EASI scores from baseline of parent study) at each visit
 - Percent change from Day 1 of current study in pruritus NRS at each week
 - Percent change from baseline of parent study in pruritus NRS at each week
 - Change from Day 1 of current study in pruritus NRS at each week
 - Change from baseline of parent study in pruritus NRS at each week
 - Proportion of patients with improvement (reduction) of pruritus NRS ≥ 4 from Day 1 of current study or achieving NRS score of 0 at each visit
 - Proportion of patients with improvement (reduction) of pruritus NRS ≥ 4 from baseline of parent study or achieving NRS score of 0 at each visit
 - Proportion of patients with improvement (reduction) of pruritus NRS ≥ 3 from Day 1 of current study or achieving NRS score of 0 at each visit

- Proportion of patients with improvement (reduction) of pruritus NRS ≥ 3 from baseline of parent study or achieving NRS score of 0 at each visit
- Proportion of patients requiring rescue treatment:
 - Overall
 - Systemic treatment
 - Systemic corticosteroids
 - Systemic immunosuppressive drugs
 - Phototherapy
- Changes from Day 1 of current study in DLQI
- Changes from baseline of parent study in DLQI
- Changes from Day 1 of current study in POEM
- Changes from baseline of parent study in POEM
- Percent changes from Day 1 of current study in POEM
- Percent changes from baseline of parent study in POEM
- Changes from Day 1 of current study in EQ-5D
- Changes from baseline of parent study in EQ-5D
- Patient global assessment of disease severity at each visit through the end of the study
- Patient global assessment of treatment effect at each visit through the end of the study

Eczema Area and Severity Index (EASI)

The EASI is a validated measure used in clinical practice and clinical trials to assess the severity and extent of AD ([Hanifin 2001](#)). The EASI score calculation is based upon the Physician's Assessment of Individual Signs [erythema (E), induration/papulation (I), excoriation (X), and lichenification (L)], where each sign is scored as 0 = Absent, 1 = Mild, 2 = Moderate, or 3 = Severe, and also upon the Area Score [based on the % (BSA) affected] where 0 = 0% BSA, 1 = 1-9% BSA, 2 = 10-29% BSA, 3 = 30-49% BSA, 4 = 50-69% BSA, 5 = 70-89% BSA, 6 = 90-100% BSA.

For each of major section of the body (head, upper extremities, trunk and lower extremities), EASI score = (E+I+X+L) x Area Score. The total EASI score is the weighted total of the section EASI using the weights 10% = head, 20% = upper extremities, 30% = trunk, 40% = lower extremities. The minimum possible EASI score is 0 and the maximum possible EASI score is 72 where a higher score indicates increased extent and severity of atopic dermatitis. The EASI score of each sign (E, I, X and L) can be calculated in a similar way, for example, the EASI score of erythema = weighted sum of E x Area Score at each section.

The EASI will be collected at the scheduled and unscheduled clinic visits as indicated in Section [10.2](#).

Investigator's Global Assessment (IGA)

The IGA is a static 5-point measure of AD disease severity used in clinical studies to determine severity of AD and clinical response to treatment. The ratings (0 = clear, 1 = almost clear, 2 = mild, 3 = moderate, 4 = severe) are an overall assessment of AD skin lesions based on erythema and papulation/infiltration. IGA score will be assessed at the scheduled and unscheduled clinic visits as indicated in Section 10.2.

Pruritus Numeric Rating Scale (NRS)

The Pruritus NRS is a simple assessment tool that patients will use to report the average intensity of their pruritus (itch), during a 1 week recall period. Patients will access the IVRS/IWRS weekly, preferably around the same time each week, and be asked the following question:

- For average itch intensity: “On a scale of 0 – 10, with 0 being ‘no itch’ and 10 being the ‘worst itch imaginable’, how would you rate your itch overall, which is on average, during the past week?”

Patients will be trained on using the IVRS/IWRS to record their Pruritus NRS score at the baseline visit, and visit 6, and will be queried by site staff for compliance at each scheduled (and any unscheduled) clinic visit.

The baseline NRS is defined as the last NRSs reported prior to the first dose of study drug.

Patient Oriented Eczema Measure (POEM)

The POEM is a 7-item, validated questionnaire used in clinical practice and clinical trials to assess disease symptoms in children and adults with atopic eczema (Charman 2004). The format is patient response to 7 items (dryness, itching, flaking, cracking, sleep loss, bleeding, and weeping) based on symptom frequency during the past week (ie, 0 = ‘no days’, 1 = ‘1 to 2 days’, 2 = ‘3 to 4 days’, 3 = ‘5 to 6’ days, and 4 = ‘every day’). The total score is the sum of the 7 items which is ranged from 0 to 28; a high score is indicative of a poor QOL. The following POEM banding scores have been established (Charman 2004): 0 to 2 = Clear or almost clear; 3 to 7 = Mild eczema; 8 to 16 = Moderate eczema; 17 to 24 = Severe eczema; 25 to 28 = Very severe eczema. If two or more response options are selected for a question, then the response option with the highest score is recorded. If one question of the seven is left unanswered, then that question is scored as 0 and the scores are summed and expressed as usual out of a maximum of 28. If two or more questions are left unanswered, then the questionnaire is not scored and is set to missing.

Dermatology Life Quality Index (DLQI)

The DLQI is a 10-item, validated questionnaire (Badia 1999) used in clinical practice and clinical trials to assess the impact of skin diseases such as AD on dermatology-related Quality of Life (QoL). Domains measured include daily activities, leisure, personal relationships, symptoms and feelings, treatment, and work and school. The format is a simple response to 10 items, which assess QoL over the last week. Each DLQI item has four response categories ranging from “Not at all” (0) to “Very much” (3). “Not relevant” is also a valid response, and it is also scored as 0. Question 7 includes a response of “Yes”, which is scored as 3. If question 7 is answered 'yes' this is scored 3 even if in the same question one of the other boxes is ticked. If question 7 is answered 'no' or 'not relevant' but then either 'a lot' or 'a little' is ticked this is then scored 2 or 1. The DLQI total score is a sum of the 10 questions. Total score ranges from 0 to 30, and higher scores indicate greater HRQOL impairment. If only one of the 10 questions is left unanswered this is scored 0 and the scores are summed and expressed as usual out of a maximum of 30. If two or more questions are left unanswered the questionnaire is not scored. If two or more response options are ticked for one question, the response option with the highest score should be recorded.

EQ-5D

The EuroQOL 5-Dimension Health Questionnaire (EQ-5D) is a standardized measure of health status developed by the EuroQol group in order to provide a simple, generic measure of health for clinical and economic appraisal (Greiner 2005). The EQ-5D as a measure of health related QOL, defines health in terms of 5 dimensions: mobility, self-care, usual activities, pain/discomfort, and anxiety/depression. Each dimension has 3 ordinal levels of severity: “no problem” (1), “some problems” (2), “severe problems” (3). Overall health state is defined as a 5-digit number. Health states defined by the 5-dimensional classification can be converted into corresponding index scores that quantify health status, where 0 represents “death” and 1 represents “perfect health.”

The 5 dimensional 3-level systems are converted into a single index utility score. Values for the 243 theoretically possible health states defined by the EuroQol classification are calculated using a regression model and weighted according to the social preferences of the UK population. The minimum value for the single index utility score is -0.594 . The Visual Analogue Scale (VAS) records the respondent’s self-rated health on a vertical visual analogue scale. The VAS ‘thermometer’ has endpoints of 100 (Best imaginable health state) at the top and 0 (Worst imaginable health state) at the bottom. This information can be used as a quantitative measure of health outcomes as judged by the individual respondents. EQ-5D self-reported VAS data generates information on the self-perceived overall health-related quality of life. [Appendix 10.4](#) provides the SAS code to derive the index utility score using UK based population.

Patient Global Assessment of Disease Status

Patients will rate their overall wellbeing based on a 5-point Likert scale. Patients will be asked: “Considering all the ways in which your eczema affects you, indicate how well you are doing”. Response choices are: “Poor” (1); “Fair” (2); “Good” (3); “Very Good” (4); “Excellent” (5).

Patient Global Assessment of Treatment Effect

Patients will rate their satisfaction with the study treatment based on a 5-point Likert scale. Patients will be asked: “How would you rate the way your eczema responded to the study medication?” Response choices are: “Poor” (1); “Fair” (2); “Good” (3); “Very Good” (4); “Excellent” (5).

The questionnaires (POEM, DLQI, and EQ-5D) will be administered only to the subsets of patients who speak fluently the languages in which the questionnaire is presented (based on availability of validated translations in participating countries).

4.6. Safety Variables

4.6.1. Adverse Events and Serious Adverse Events Variables

The primary endpoint in the study is the incidence and rate (events per patient-year) of treatment-emergent adverse events (TEAEs) through the last study visit.

The key secondary endpoints related to AE is

- Incidence and rate (events per patient-year) of SAEs and AEs of special interest

Adverse events and serious adverse events will be collected from the time of informed consent signature and then at each visit until the end of the study. All adverse events are to be coded to a “Preferred Term” and associated primary “System Organ Class (SOC)” according to the Medical Dictionary for Regulatory Activities (MedDRA, latest version).

An **Adverse Event** is any untoward medical occurrence in a patient administered a study drug which may or may not have a causal relationship with the study drug. Therefore, an AE is any unfavorable and unintended sign (including abnormal laboratory finding), symptom, or disease which is temporally associated with the use of a study drug, whether or not considered related to the study drug.

AEs also include: any worsening (i.e., any clinically significant change in frequency and/or intensity) of a pre-existing condition that is temporally associated with the use of the study drug; abnormal laboratory findings considered by the investigator to be clinically significant; and any untoward medical occurrence.

A **Serious Adverse Event** is any untoward medical occurrence that at any dose results in death; is life-threatening; requires in-patient hospitalization or prolongation of existing hospitalization; results in persistent or significant disability/ incapacity; is a congenital anomaly/ birth defect; or is an important medical event.

The criteria for determining whether an abnormal laboratory, vital sign or ECG finding should be reported as an AE are as follows:

- Test result is associated with accompanying symptoms, and/or
- Test result requires additional diagnostic testing or medical/surgical intervention, and/or
- Test result leads to a change in dosing (outside of protocol-stipulated dose adjustments) or discontinuation from the study, significant additional concomitant drug treatment, or other therapy

The pre-treatment period is defined as the period from the subject providing informed consent up to the first dose of study drug in current study.

The treatment period is the period starting from the first dose date up to the last dose date + 7 days. As there are two gaps in treatment due to protocol amendment 7 and 8, the gaps in treatment are not included as part of the treatment period.

The follow-up period is the period starting 1 day after end of treatment period up to the end of study visit. As some patients were allowed to complete the follow-up period under protocol amendment 6 then re-enter the study, or were allowed to complete the follow-up period under protocol amendment 7 and then re-enter the study, the follow-up period consists of all the separate follow-up periods under protocol amendment 6, 7 and 8.

The overall study period consists of treatment and follow-up period.

The pre-treatment AE and treatment emergent AE (TEAE) are defined as following:

- Pre-treatment signs and symptoms (Pre-treatment AEs) are AEs that developed or worsened in severity during pre-treatment period.
- Treatment-emergent AEs (TEAEs) are AEs that developed or worsened in severity compared to the Day 1 of current study during the treatment and follow-up period. As the protocol indicated that only the worsening pre-existing AEs and new AEs reported during the treatment and follow-up period will be collected in the study, all AEs with onset during the treatment and follow-up period are considered as TEAEs. So TEAE includes all AE onset during the treatment period and during follow-up period.

Under protocol amendment 7, patients in France, Germany, Poland and Japan who had completed their end of study visit under protocol amendment 6 were permitted to re-enter the study. Similarly, under protocol amendment 8, patients in Poland, Finland and France who had already completed their end of study visit under protocol amendment 7 were permitted to re-enter the study.

Treatment discontinuation required under protocol amendment 6 followed by resumption of treatment permitted under protocol amendment 7 resulted in a gap in treatment for certain patients in these four countries. There was a similar treatment gap for certain patients in Poland, Finland and France who had an EoT/EoS visit under amendment 7 and subsequently resumed treatment under amendment 8.

Hence any AE with an onset between the end of study visit under protocol amendment 6 and the date of first injection under amendment 7; or between end of study visit under protocol amendment 7 and date of first injection under amendment 8 is **not** considered TEAEs.

The list of adverse events of special interest (AESI) was revised several times. Below is the AESI list under protocol amendments 4 and 5:

- Anaphylactic reactions
- Acute allergic reaction
- Severe injection site reactions that last longer than 24 hours
- Mycosis fungoides
- Cutaneous T-cell dyscrasia
- Any severe infection
- Any infection requiring treatment with parenteral antibiotics
- Any infection requiring treatment with oral antibiotics/anti-viral/anti-fungal for longer than 2 weeks
- Any clinical endoparasitosis
- Any opportunistic infection

Under protocol amendment 6, suicide-related events and certain eye-related events were added as AESIs. Under protocol amendment 7, the list of AESI are as follows:

- Anaphylactic reactions
- Systemic or extensive hypersensitivity reactions
- Malignancy (except basal cell carcinoma)
- Helminthic infections
- Any suicide-related events
- Any type of conjunctivitis or blepharitis, or keratitis (severe or serious)

The SAP summarizes AESIs according to the most current list under protocol amendments 7 and 8. The definition of AESI is same under protocol amendment 7 and 8.

[Appendix 10.6](#) provides a list of AESIs search criteria.

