Anaphylactic reactions	For SMQ “anaphylactic reaction” An algorithmic approach will be used. A case must include either: 4. A narrow term (a term from Category A); 5. Patient with both a term from Category B AND a term from Category C ; 6. Patient with a term from Category D AND { a term from Category B - OR a term from Category C } For bullets 2 and 3, the search terms that are included under the SMQ for a particular event need to have the same start date (for e.g. if search shows cough (category B term) occurring at day 3 and urticaria (category C term) occurring at day 7, this event is not adjudicated as anaphylactic reaction as this is inconsistent with the clinical presentation of anaphylaxis as an acute event with simultaneous involvement of 2 or more body systems. Note: manual adjudication of relevant PTs will be required by the study medical monitor, before database lock

AESI	Search Criteria
Systemic or severe hypersensitivity reactions	
Hypersensitivity: Narrow SMQ for hypersensitivity excluding preferred term equal to dermatitis atopic or eczema
 
For systemic hypersensitivity, events in which 2 or more body systems are involved (as defined by System Organ Class) would be considered for adjudication based on further medical judgement
 
For severe hypersensitivity, an additional search will be done;
 
 - HLT = Injection site reactions - Severity = “severe” 
Note: manual adjudication of relevant PTs will be required by the study medical monitor, before database lock

Malignancy	
 • SMQ “Malignant tumours” • SMQ “Tumours of unspecified malignancy”
Helminthic infections	
-HLT = Cestode infections
 
-HLT = Helminthic infections NEC
 
-HLT = Nematode infections
 
-HLT = Trematode infection

Suicidal behavior	
Include the following PTs
 
 • Completed suicide • Suicidal ideation • Suicide attempt • Depression suicidal • Suicidal behavior

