Any type of conjunctivitis or blepharitis or keratitis (only events that are either severe or serious)	
broad CMQ conjunctivitis (Conjunctivitis, Conjunctivitis allergic, Conjunctivitis bacterial, Conjunctivitis viral, Atopic keratoconjunctivitis, Blepharitis, Dry eye, Eye irritation, Eye pruritus, Lacrimation increased, Eye discharge, Foreign body sensation in eyes, Photophobia, Ocular hyperaemia, Conjunctival hyperaemia, Xerophthalmia);
 
Blepharitis PTs (Blepharitis, blepharitis allergic);
 
Keratitis PTs (Keratitis, Allergic keratitis, Ulcerative keratitis, Atopic keratoconjunctivitis, Herpes ophthalmic, Ophthalmic herpes simplex);
 
AND
 
 • Serious AE= “Yes” OR Severity= “severe” 
Note: manual adjudication of relevant PTs will be required by the study medical monitor, before database lock.

¹ The search criteria are meant to assist the process of identification of TEAE of Special Interest/TEAE Syndrome. However, since these criteria might not be exhaustive in some cases or may not be specific in other cases. Hence an additional review of all PTs in the database may be performed by the Medical monitor, based on medical judgement, to identify any TEAE of Special Interest/TEAE Syndrome that might have been missed by the criteria or to identify any TEAE may be inaccurately assigned as AESI by the algorithmic search

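### The AESI search table in SAP Appendix 10.6 does not carry out the definitions in SAP 4.6.1: the malignancy row omits the basal cell carcinoma exception, and the hypersensitivity row has *severe* where the definition has *extensive*

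*SAP*

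**What the plan says.** SAP 4.6.1 makes "Incidence and rate (events per patient-year) of SAEs and AEs of special interest" a key secondary endpoint. It records that the AESI list changed several times and settles which one applies: "The SAP summarizes AESIs according to the most current list under protocol amendments 7 and 8". Two of the six entries on that list matter here: "Malignancy (except basal cell carcinoma" and "Systemic or extensive hypersensitivity reactions". The section then refers to Appendix 10.6 for the search criteria.

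In the Appendix 10.6 table for amendments 6, 7 and 8:

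- The malignancy row consists of two SMQs taken whole, one for malignant tumours and one for "Tumours of unspecified malignancy". It has no exclusion and no adjudication note.
- The hypersensitivity row is titled "Systemic or severe hypersensitivity reactions". It starts from the narrow hypersensitivity SMQ and removes two named preferred terms (PTs). It then describes the systemic limb as involvement of at least two body systems. For the severe limb it adds a search for injection-site reactions graded severe. Manual adjudication by the medical monitor before database lock is mandatory.
- The table footnote describes the criteria as an aid to identification and says that "an additional review of all PTs in the database may be performed by the Medical monitor". The purpose is to find missed events and events wrongly assigned.

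SAP 5.8.1 reports events per 100 patient-years (NEPY) and the exposure-adjusted patient rate (EAIR) for AESIs, by AESI category and by high-level and preferred term.

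**The concern.** A definition and the search that implements it should return the same events. Here they can differ in two of the six categories. A programmer who follows 4.6.1 and one who follows the Appendix 10.6 rows could produce different AESI tables from the same data, with nothing in the SAP to settle which is right except a review that need not happen.

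For malignancy the risk runs one way. An event that the definition leaves out can be counted, and no mandatory step takes it out again. For hypersensitivity the direction is mixed. An extensive reaction confined to one body system has no stated criterion under which it qualifies, while severe injection-site reactions enter a category whose definition does not mention them. The trial's purpose is long-term safety, so the content of each AESI category is part of what it reports.

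**Working it through.** The plan states no AESI count, rate or precision on this point, so there is no figure to reproduce. The check compares the texts and then gives a scale.

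**Step 1. Definition against search row**

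| | SAP 4.6.1 | Appendix 10.6, amendments 6/7/8 | Adjudication required in row |
|---|---|---|---|
| Malignancy | Basal cell carcinoma excepted | Two whole SMQs, no exclusion | No |
| Hypersensitivity | Systemic or extensive | Narrow SMQ less two PTs; systemic = at least two body systems; severe = severe injection-site reactions; no rule for extensive | Yes |

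**Step 2. Is the missing exclusion only shorthand?** The table writes filters into its rows elsewhere. The hypersensitivity row names the PTs it removes, and the eye row carries its serious-or-severe condition. The anaphylaxis, hypersensitivity and eye rows require adjudication. The malignancy, helminth and suicide rows do not, and of those three only malignancy has an exception in its definition. The amendment 7 rationale in the protocol also introduces malignancy with the exception attached, so the exception was deliberate.

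**Step 3. Can such events arise?** Protocol 4.2.2 (criterion 15) admits patients with completely treated, resolved basal cell carcinoma. Protocol 5.2.2.1 leaves basal cell carcinoma out of the malignancies that require permanent discontinuation. Patients with a new one can therefore remain under observation. How many there were is not stated.

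**Step 4. Injection-site reactions.** The amendment 4/5 table had its own row for these, requiring severe grade and duration over 24 hours. The amendment 7 rationale says they no longer need heightened surveillance, and the amendment 7/8 list omits them. The later search brings back the severe ones with no duration limit, inside another category.

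**Step 5. Effect on the rates.** By Appendix 10.5, NEPY = 100 × Σnᵢ / Σtᵢ and EAIR = 100 × n / Σtᵢ, with a patient's time in the EAIR stopping at the first event. A wrongly included event raises both numerators and also shortens the EAIR denominator.

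**Step 6. Scale only.** N = 2678 enrolled (SAP 2.2), used in place of the treated number. The number k of wrongly included patients, with one event each, and the mean exposure are assumptions.

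- Added incidence = 100 × k / 2678: k = 1 gives 0.037, k = 5 gives 0.187, k = 10 gives 0.373 and k = 20 gives 0.747 percentage points.
- Added NEPY for k = 10 = 1000 / (2678 × mean years): 0.373, 0.187 and 0.124 per 100 patient-years for means of 1, 2 and 3 years.

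**The case against.** The strongest reply is that 4.6.1 controls. It names the governing list, and that list excepts basal cell carcinoma. The Appendix 10.6 footnote says that the table only assists identification and foresees a review of all PTs in both directions. AESIs are displayed down to PT, so a counted basal cell carcinoma would be visible, and severe injection-site reactions would appear under their own high-level term. The analysis is descriptive, with no hypothesis test.

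Most of this stands as a limit on the harm. It does not close the gap, because the footnote review is optional and visibility at PT level does not correct the category total.

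On hypersensitivity, a reader might infer that severe injection-site reactions have replaced the hypersensitivity search, or that single-system reactions can never reach the adjudicator. The text supports neither. The narrow SMQ stays as the base, and the injection-site search is described as additional. The two-system sentence concerns the systemic limb, while the adjudication note for the row carries no such limit. What remains is that *extensive* has no criterion, and that the row includes a search for events outside its definition.

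**Conclusion.** The mismatch is real and should be corrected. In the malignancy row, the search as written departs from the definition and has no mandatory step to put that right, so the category can be over-counted in incidence, NEPY and EAIR. In the hypersensitivity row, one defining word has been changed and left without a criterion, and a type of event not on the governing list has been added, under adjudication that is at least compulsory.

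The size is unknown. That the two SMQs capture basal cell carcinoma is an assumption. The written exception suggests it, but SMQ contents are not in the documents, and neither are counts of basal cell carcinoma or severe injection-site reactions. A reader might infer that the key secondary AESI rate is in fact miscounted, or might apply an inflation factor of 1/(1 − share). Shares of 20% and 60% would give 1/0.8 = 1.25 and 1/0.4 = 2.5. The documents support no share, and the factor would apply to one category of six. They support a risk of over-counting malignancy and an unclear content for hypersensitivity, not a demonstrated error.

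**What to change.** In the amendment 6/7/8 table of Appendix 10.6:

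- **Malignancy row.** Exclude basal cell carcinoma PTs, and add the mandatory adjudication note that the anaphylaxis, hypersensitivity and eye rows already have.
- **Hypersensitivity row.** Use the 4.6.1 term in the title. Send all narrow-SMQ hits left after the stated PT exclusions, including single-system events, to the adjudication already required. The study team should write down what counts as extensive, since neither document says. Tabulate severe injection-site reactions outside this AESI category.

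For analyses under amendment 10, bring both the list and the search table into line with protocol 7.2.3. That section no longer lists malignancy, lists only systemic hypersensitivity reactions, and makes certain injection-site reactions an additional AESI for the sub-study. SAP section 7 already foresees an addendum for later analyses, which is the natural place for this.

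The cost is a few lines of appendix text and a longer adjudication listing for hypersensitivity, whose length cannot be judged from the documents. No new data collection is needed.
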